## 7.4.8 Urine Pregnancy Test

A urine pregnancy test will be performed at each clinic visit (except for visit 5) throughout the trial. The test should always be performed before ring insertion / removal at RM+7 visits of the treatment period. If the test result is positive, a serum  $\beta$ hCG test must be performed. If both test results are positive, the subject will be discontinued from the trial.

## 7.4.9 Urine Drug Screen

A urine drug screen will be performed locally as part of eligibility check before entry into run-in (before or at visit 1) and prior to randomization at visit 4. The drug screen will be performed from fresh mid-stream urine for the determination of amphetamines / methamphetamine, barbiturates, benzodiazepines, cocaine, methylenedioxymethamphetamine, methadone, opiates, oxycodone, phencyclidine, tetrahydrocannabinol and tricyclic antidepressants. Subjects with a positive drug screen should be excluded unless the cause is from opioids or antidepressants that are medically indicated and prescribed by a physician.

## 7.4.10 Luteinizing Hormone Surge

LH kits will be dispensed to subjects at visits 1 and 7 for the assessment of LH surge during cycles -1 and 4. Instructions on LH surge testing and reminders of LH surge testing will be given.

### 7.4.11 Physical Examination

A complete physical examination will be performed before entry into run-in (before or at visit 1), and at end-of-treatment / cycle 4 (at visit 10). Information will be recorded for general appearance,

central and peripheral nervous system, head and neck (including ears, eyes, nose, mouth and throat), respiratory system, cardiovascular system, gastrointestinal system, lymphatic system, urinary system, musculoskeletal system and skin.

Before entry into run-in (baseline), each category will be evaluated as normal, abnormal not clinically significant or abnormal clinically significant. Abnormal clinically significant findings at baseline must be reported on the Medical History Log.

At cycle 4 / end-of-treatment, potential changes from baseline to cycle 4 or to end-of-treatment will be evaluated for each category. In case of changes, these will be evaluated as normal, abnormal not clinically significant or abnormal clinically significant. Abnormal clinically significant changes from baseline must be recorded as adverse events.

## 7.4.12 Gynecological and Pelvic Examination

A complete gynecological examination will be performed by the investigator before entry into runin (before or at visit 1), and at end-of-treatment / cycle 4 (at visit 10). Information will be recorded for breast, external genitalia, vagina, cervix, uterus, uterine adnexa (including ovaries and fallopian tubes) and cul-de-sac.

Before entry into run-in (baseline), each category will be evaluated as normal, abnormal not clinically significant or abnormal clinically significant. Abnormal clinically significant findings at baseline must be reported on the Medical History Log.

At cycle 4 / end-of-treatment, potential changes from baseline to end-of-treatment will be evaluated for each category. In case of changes, these will be evaluated as normal, abnormal not clinically significant or abnormal clinically significant. Abnormal clinically significant changes from baseline must be recorded as adverse events.

In connection with the B&B scale scoring, an examination of pelvic tenderness and pelvic induration will be performed by the investigator at randomization and at cycle 4 (see section 7.2.2.1). The pelvic examination at cycle 4 is also part of the gynecological examination at cycle 4.

## 7.4.13 Cervical Swab

As part of eligibility check, a single swab will be obtained from the endocervical area before entry into run-in (before or at visit 1) for assessing gonorrhea and chlamydia. Subjects with positive test results must be excluded. Standard reporting and referral procedures at the sites will be followed in line with local regulations.

## 7.4.14 Transvaginal Ultrasound

A transvaginal ultrasound will be performed by an experienced sonographer before entry into run-in (before or at visit 1), and at end-of-treatment / cycle 4 (at visit 10). The transvaginal ultrasound will

assess uterus, endometrium and ovaries to evaluate endometrial thickness, number and size of endometrioma(s), ovarian cyst(s) and fibroid(s) if presented.

Endometrial thickness (composed of both layers of the endometrium) will be measured in the sagittal view of the uterus from the proximal and distal interfaces between the echogenic endometrium and the hypoechoic inner layer of the myometrium. Care should be taken not to include the presence of any fluid in the uterine cavity in calculating the endometrial thickness value. Endometrial thickness will be recorded in mm.

Endometrioma, fibroid and ovarian cyst will be recorded as observed or not. If observed, the number and size of endometrioma(s), fibroid(s) and ovarian cyst(s) should be recorded.

## 7.4.15 Vital Signs

Systolic and diastolic blood pressure as well as pulse will be measured before entry into run-in (before or at visit 1), prior to randomization at cycle -1, during cycle -1 and at end-of-treatment / cycle 4 (at visit 4, 5 and 10). Vital signs at randomization will be baseline. Blood pressure and pulse should be measured before blood sampling as applicable, by automated oscillometric device sequentially, first after the subject is in supine position for at least 3 minutes, then in seated position for at least 3 minutes, and then at 1 minute and at 3 minutes after standing. Changes in blood pressure will be calculated using the minimum standing measurement minus the seated measurement and minus the supine measurement, respectively.

The investigator will review the results of vital signs and evaluate and document whether the finding is clinically significant or not.

Before entry into run-in (before or at visit 1) and before randomization (at visit 4), subjects with a drop of 20 mmHg of systolic blood pressure or a drop of 10 mmHg of diastolic blood pressure from sitting to standing will be excluded from the trial.

At other visits (visits 5 and 10), a drop of 20 mmHg of systolic blood pressure or a drop of 10 mmHg of diastolic blood pressure from lying to standing or from sitting to standing is considered clinically significant and will be reported as adverse events.

# 7.4.16 Columbia-Suicide Severity Rating Scale (C-SSRS)

The C-SSRS is a screening tool to assess the potential risk of suicidality. It is implemented in this trial to meet the US regulatory requirements for all neurologic drugs with central nervous system activity, even though quinagolide has not been shown to be associated with suicidal ideations during its marketing experiences of more than 20 years in Europe.

The electronic C-SSRS (eC-SSRS) will be self-administered through the interactive voice response (IVR) phone system (with a web portal as a back-up solution) before entry into run-in (before or at visit 1), prior to randomization at cycle -1, at cycles 2 and 4 (at visits 4, 7 and 10). The results of

eC-SSRS will be reviewed by investigators and delegated trial staff to assess the potential risk of suicidality, including suicidal ideations of type 4 (active suicidal ideations with some intent to act, without specific plan), suicidal ideations of type 5 (active suicidal ideations with specific plan and intent) and suicidal behavior.

Before entry into run-in (before or at visit 1), subjects having suicidal ideations of type 4 or type 5 during the past 12 months or having suicidal behavior during the past 5 years as identified by the eC-SSRS will be excluded from the trial. Prior to randomization at visit 4, subjects having suicidal ideations of type 4 or type 5 or having suicidal behavior since last e-CSSRS assessment will also be excluded from the trial. It is the investigator's responsibility to advise subjects excluded from the trial due to risk of suicidality to seek help from their own physicians or suicide prevention services.

During the treatment (at visits 7 and 10), subjects having suicidal ideations of type 4 or type 5 or having suicidal behavior as identified by the eC-SSRS should be referred to a mental health professional for further assessment and/or treatment. The decision on whether the treatment should be discontinued is to be taken by the investigator in consultation with the mental health professional to whom the subject is referred.

## 7.4.17 Concomitant Medication

The use of any concomitant medication within the last 3 months prior to informed consent for participation in the trial and throughout the trial will be recorded. Recording of concomitant medication other than ibuprofen and hydrocodone-acetaminophen will be performed at all visits. Any changes in concomitant medications or treatments must be recorded at each visit. Investigators' instructions for ibuprofen dosing and prescriptions of hydrocodone-acetaminophen will be recorded in the e-CRF.

### 7.4.18 Drug Accountability

For all vaginal rings, date and time of insertion and removal at the clinics will be recorded. Furthermore, the dates and amount of ibuprofen dispensed and returned will be recorded in the IRT system. Details on drug dispensing and accountability are provided in section 5.6.

## 7.4.19 End-of-Treatment Question

All subjects, irrespective of whether they completed the treatment or not, will be asked which treatment group (placebo or quinagolide) they believe they were randomized to at the end of treatment. The question can be phrased as "Do you think you were on a ring with study drug or a ring with placebo (i.e. no study drug)?"

## 7.4.20 End-of-Treatment Form

An end-of-treatment form should be filled in at the subject's end-of-treatment visit, irrespective of whether the subject completes the treatment or not. Completion / discontinuation status will be recorded, as well as date and reason for discontinuation in case the subject does not complete the treatment.

## 7.4.21 End-of-Trial Form

An end-of-trial form should be filled in at the subject's last visit, irrespective of whether the subject completes the trial or not. Completion / discontinuation status of the follow-up period will be recorded.

## 7.4.22 Optional Pharmacogenetic Analysis

If the subject has provided a separate written informed consent for genetic testing (see section 14.5), a sample of whole blood for extraction and analysis of DNA will be collected within 1-5 days of the first ring insertion during cycle 1 (at visit 5). The informed consent for genetic testing signed by the subject must be obtained prior to the sampling. All samples will be analyzed for the presence of polymorphisms in the cytochrome P450 2D6 (CYP2D6) gene, which codes for an enzyme involved in the metabolism of quinagolide.

Additional analysis of other enzymes involved in the elimination processes of quinagolide may be performed on samples from subjects who display quinagolide metabolite M1 concentrations at similar levels as the parent compound and on a comparable number of control samples from subjects with low levels of metabolites (M1<20% of quinagolide levels). Only enzymes responsible for the elimination processes (i.e. metabolism, transportation and excretion) of quinagolide will be analyzed. Results of the pharmacogenetic analysis will not be provided to the sites.

## 7.4.23 **Optional Patient Interviews**

A sub-group of 60 subjects including 5 non-completers from selected sites, if they have provided a separate informed consent, will be invited to a patient interview at the end of treatment to help determine the meaningful treatment benefit from the patients' perspective and to assess the content validity of the questions related to daily functioning in the e-Diary. The timing of the interview, i.e. within 2 weeks of subjects' completion of or discontinuation from the treatment (visit 10), allows for both subjects on active treatment and subjects on placebo to report their treatment experiences.

Subjects will be asked open-ended questions about the changes they have experienced since the start of the trial, and about the nature and relevance of these changes by following a semi-structured interview guide and a patient interview protocol. In addition, the content validity of the daily functioning questions in the e-Diary will be assessed. The interviews will be conducted in English over the telephone by a trained interviewer from Evidera, a third-party CRO in the United States.

All interviews will last for approximately 2 hours, and will be audio-recorded. All subjects participating in the patient interview will be identified by using the same subject identification number of this trial to guarantee data protection. Both subjects and interviewers will be blinded to treatment allocation. Results of the patient interviews will be reported separately.

## 7.5 Handling of Biological Samples

Trial-specific laboratory manuals will be provided to the participating sites, describing in detail how to handle, store and transport the biological samples (blood) in this trial. All blood samples collected during the trial will be analyzed at central laboratories and will be destroyed within 2 years after reporting of the trial. Exceptions are the blood samples collected for potential future endometriosis biomarkers and for potential analyses of circulating cell-free DNA and microRNA; these will be stored for a maximum of 10 years after reporting of the trial prior to destruction in line with local regulations. For all biological samples collected in the trial, it applies that any analyses beyond those described in the protocol will be performed only after obtaining the required approvals. The processes related to handling of biological samples will be described in the informed consent documents, and the biobank / data protection legislations including local legislation will be adhered to.

#### 8 ADVERSE EVENTS

#### 8.1 Adverse Event Definition

An adverse event is any untoward medical occurrence in a subject participating in a clinical trial. It includes:

- Any unfavorable and unintended sign, symptom or disease temporally associated with the use of the IMP, whether or not considered to be caused by the IMP.
- Adverse events commonly observed and adverse events anticipated based on the pharmacological effect of the IMP.
- Any laboratory abnormality, vital signs, ECG, echocardiography or finding from physical or gynecological examination including transvaginal ultrasound assessed as clinically significant by the investigator [*note*: findings from assessments and examinations done during the screening period are not adverse events, but are recorded as medical history.]
- Accidental injuries, reasons for any medical, nursing or pharmacy consultation, or reasons for admission to hospital or surgical procedures.

All adverse events will be coded by Ferring Pharmacovigilance using MedDRA (the MedDRA version will be documented).

Medication errors of IMP will be captured by ring acceptability questionnaire and/or a medication error form in the e-CRF.

### 8.2 Collection and Recording of Adverse Events

#### 8.2.1 Collection of Adverse Events

The investigator must monitor the condition of the subject throughout the trial from the time of obtaining informed consent until the end-of-trial visit.

The sources of adverse events cover:

- The subject's response to questions about her health (a standard non-leading question such as "How have you been feeling since your last visit?" is asked at each visit).
- Symptoms spontaneously reported by the subject.
- Investigations and examinations where the findings are assessed by the investigator to be clinically significant changes or abnormalities.
- Other information relating to the subject's health becoming known to the investigator (e.g. hospitalization).

## 8.2.2 Recording of Adverse Events

The investigator must record all adverse events in the Adverse Event Log provided in each subject's e-CRF with information about:

- Adverse event
- Date and time of onset (time can be omitted, if applicable) [*note*: if date of onset of an event is the same as the date of informed consent or date of IMP administration, time is important and should not be omitted]
- Intensity
- Causal relationship to IMP
- Action taken to IMP
- Other action taken
- Date and time of outcome (time can be omitted, if applicable)
- Outcome
- Seriousness

Each of the items in the Adverse Event Log is described in detail in the following sections.

#### **Adverse Event**

Adverse events should be recorded as diagnoses, if available. If not, separate signs and symptoms should be recorded. One diagnosis / symptom should be entered per record.

If a subject suffers from the same adverse event more than once and the subject recovers in between the events, the adverse events should be recorded separately. If an adverse event changes in intensity, a worst-case approach should be used when recording the event, i.e. the highest intensity and the longest duration of the event.f

*Note*: A procedure is not an adverse event; the reason for conducting the procedure is. Hospitalization is not an adverse event; the reason for hospitalization is. Death is not an adverse event, but the cause of death is (an exception is sudden death of unknown cause, which is an adverse event).

#### Date and Time of Onset

The date of onset is the date when the first sign(s) or symptom(s) were first noted. If the adverse event is an abnormal clinically significant laboratory test or outcome of an examination, the onset

<sup>f Exception: if an adverse event with onset before the first IMP administration (i.e. a pre-treatment adverse event) changes in intensity after the IMP administration, this must be recorded as two separate events. The initial adverse event should be recorded with outcome "not recovered" and the date and time of outcome is when the intensity changed. The second adverse event should be recorded with date and time of onset when the intensity changed.

date is the date the sample was taken or the examination was performed.

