#### Intensity

The intensity of an adverse event must be classified using the following 3-point scale:

Mild:	Awareness of signs or symptoms, but no disruption of usual activity.
Moderate:	Event sufficient to affect usual activity (disturbing).
Severe:	Inability to work or perform usual activities (unacceptable).

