### Outcome

The outcome of an adverse event must be classified as one of the following:

- Recovered (fully recovered or the condition has returned to the level observed at initiation of trial treatment)
- Recovered with sequelae (resulted in persistent or significant disability/incapacity)
- Recovering (the event is improving)
- Not recovered
- Fatal

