10.1 General Considerations

Safety parameters will be evaluated for the safety analysis data set.

All safety summaries will be performed by treatment:

For adverse events (AE) and concomitant medications the following rules will apply;

Treatment period	AE and concomitant medications to be included
Part A	Start after start of IMP, and start date before or equal to the date of the end-of-cycle 4 visit, if missing use date of premature discontinuation
Part B	Start date after the date of the end-of-cycle 4visit and before or equal to date last ring removal, if missing use date of premature discontinuation.

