10.2 Adverse Events

AEs are classified according to MedDRA version 20.0.

Written narratives will be issued for all serious AEs (including deaths) and AEs leading to withdrawal.

A pre-treatment adverse event is any adverse event occurring after signed informed consent and before start of IMP or a pre-existing condition that worsens in intensity after signed informed consent but before start of IMP. Pre-treatment AEs will be presented in a separate data listing only.

A treatment-emergent adverse event (TEAE) is any adverse event occurring after start of IMP and before the end-of-trial visit, or a pre-treatment adverse event or pre-existing medical condition that worsens in intensity after start of IMP and before the end-of-trial visit.

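### Footnote f splits a pre-treatment adverse event on any change in intensity, so one that eases but persists after the first ring can be counted as treatment-emergent

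*Protocol*

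**What the plan says.** Protocol section 8.2.2 gives a general rule for an adverse event whose intensity varies: "a worst-case approach should be used when recording the event, i.e. the highest intensity and the longest duration of the event". That produces one record. Footnote f is the exception for events with onset before the first ring. If such an event "changes in intensity after the IMP administration, this must be recorded as two separate events". The first record is closed as not recovered on the date of the change. For the other: "The second adverse event should be recorded with date and time of onset when the intensity changed".

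On grading, the same section says: "The intensity of an adverse event must be classified using the following 3-point scale". The grades are mild, moderate and severe.

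The treatment-emergent definition is the same in protocol section 9.8 (footnote g) and SAP 10.2, and it has two parts. The first is "any adverse event occurring after start of IMP and before the end-of-trial visit". The second brings in a pre-treatment event or pre-existing condition only if its intensity worsens after the start of treatment and before the end-of-trial visit. SAP 10.2 sends pre-treatment events to a separate listing and to no table.

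SAP 10.1 assigns events to treatment periods by date. For Part A the rule is: "Start after start of IMP, and start date before or equal to the date of the end-of-cycle 4 visit", with the date of premature discontinuation used if that visit is missing.

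**The concern.** The recording rule and the counting rule use different triggers. Footnote f acts on a change in either direction, while the definition treats a pre-treatment event as emergent only when it gets worse. Once the event has been split, the second record stands as an event of its own with an onset after the first ring. It can then qualify under the first part of the definition without the worsening condition ever being applied.

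At stake is the meaning of the treatment-emergent tables in SAP 10.2.2. Partial relief of a complaint that predates treatment could appear there as a new event, for example among the mild ones. The SAP plans no statistical analysis, so the safety evidence is these descriptive counts together with the listings.

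**Working it through.** No figure in the plan depends on this point, so the check applies the rules as written to two cases. The dates are assumed for illustration.

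**Case A, easing.** A moderate event starts on day -10, after consent, and eases to mild on day +3 without resolving.

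1. Is footnote f triggered? Yes. Moderate to mild is a change on the 3-point scale, and the change follows the first ring.
2. What is recorded? Record 1: moderate, onset day -10, not recovered, outcome date day +3. Record 2: mild, onset day +3.
3. Does record 2 meet the first part of the definition? Yes, because its onset is after the start of treatment.
4. Does it meet the SAP 10.1 date rule for Part A? Yes.
5. Does the event meet the second part of the definition? No, because it did not worsen.
6. Does any rule remove record 2? None was found in either document.

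Result as written: 1 subject and 1 event in the treatment-emergent tables. If footnote f applied only to worsening, the event would stay as one moderate pre-treatment record and contribute 0.

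**Case B, worsening.** A mild event becomes severe on day +3. It is split, record 2 has on-treatment onset, and both parts of the definition are met. Result: 1 treatment-emergent event under either wording of the footnote.

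The two wordings differ only in case A, which is where the two parts of the definition disagree.

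Two features suggest that the footnote was written with worsening in mind. It forces the first record to be closed as not recovered, although the outcome list in section 8.2.2 has a separate category for an event that is improving. Section 8.2.2 also dates onset from the first appearance of signs or symptoms, and an easing symptom has no such new appearance.

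The affected pool is narrow. The event must start after consent, be ongoing at first insertion, drop at least one grade and persist. An event that resolves is closed as recovered. Findings from screening examinations go to medical history (protocol 8.1). Endometriosis-related pain, menstrual cramp and dyspareunia are not adverse events unless serious (8.3.3), and abnormal bleeding is reported only if it needs intervention or is serious (8.3.4).

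**The case against.** The strongest reply is that the definition has a part written specifically for pre-treatment events, that this part requires worsening, and that the specific should govern the general. On that reading a continued pre-treatment event that improves is not emergent, however many records it occupies. The SAP 10.1 table, moreover, allocates events to Part A or Part B and does not define emergence. This is a reasonable reading, and no sentence in either document says that improved events are treatment-emergent. What stands is that the event *can* be counted, not that it must be. The reply does not remove the point, because footnote f makes the second record a separate event and nothing tells a programmer to apply the worsening test to it.

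A reader might also infer that the second record cannot be traced to the first, since the Adverse Event Log items in section 8.2.2 include no explicit link. The documents do not support that. Footnote f makes the outcome date of the first record equal to the onset date of the second, so the pair can be found from logged items.

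A reader might further infer that the tables of related events are inflated, because an onset soon after insertion looks causal. That is speculation. Section 8.2.2 asks for evidence or argument before causality is accepted, and nothing shows that an investigator who re-enters an easing complaint would attribute it to the ring.

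Finally, the rule applies in every arm, summaries are by treatment, and all adverse events are listed. No test, error rate or efficacy estimate is affected. All of that stands and limits the importance of the point.

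**Conclusion.** The concern holds as an inconsistency between the recording rule and the treatment-emergent definition. Read literally, footnote f with the first part of the definition and the SAP start-date rule lets an easing pre-treatment event enter the treatment-emergent counts and intensity tables, contrary to the second part of the definition. It merits correction because it bears on what the tables mean and the remedy is small.

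The size cannot be estimated. The documents give no rate of ongoing pre-treatment events and no rate of easing. A reader might assume such rates, multiply by the planned 70 women per arm and compare the result with the 5% display threshold (0.05 x 70 = 3.5, so 4 women). That comparison is not supported. The 5% table is by preferred term, whereas such a count would pool all event types. The SAP reports early termination with a low number of subjects, so 70 is only a planned size. A woman with any other treatment-emergent event adds nothing to overall incidence.

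One assumption remains. The footnote checked is in protocol version 6.0, while SAP section 1 says that most women were randomized under version 5.0. The conclusion for them assumes the same recording rule.

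**What to change.** In SAP 10.2, add a sentence stating that a split record continuing a pre-treatment adverse event at the same or lower intensity is not treatment-emergent. Identify such pairs before database lock by three conditions:

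- the same subject and preferred term;
- the first record's outcome date equal to the second record's onset date;
- the first record's outcome given as not recovered.

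For consistency, and for any future use of the protocol text, limit footnote f to events that worsen in intensity, to match footnote g. In this trial that change alone would not help. The SAP was written after early termination, and a new word in the footnote cannot alter records already entered.

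The cost is a small amount of programming and a review of the matched pairs. The pairs should be looked at rather than dropped automatically. The first record holds the highest pre-treatment intensity, so an event that had already eased before insertion and then worsened could look like an improvement on the recorded grades alone.
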